# **B) Secondary Outcome Measures:**

- 1) Pain intensity [Time Frame: T1, 30 minutes before the procedure (patient's room); T2, upon arrival at the hydrotherapy room; T3, 10 min after the beginning of the hydrotherapy session; T4, immediately after the session before leaving hydrotherapy room; T5, 30 min. after the session]: Face, Legs, Activity, Cry and Consolability (FLACC).
- 2) Anxiety Level [Time Frame: T2, upon arrival at the hydrotherapy room; T3, 10 min after the beginning of the hydrotherapy session; T4, immediately after the session before leaving hydrotherapy room; T5, 30 min. after the session]: Procedure Behaviour Check List (PBCL).

- 3) Comfort Level [Time Frame: T3, during the procedure (10 min after the beginning of the hydrotherapy session)]: Behavioural observation scale of comfort level for child burn victims (OCCEB- BECCO).
- 4) Analgesic requirement [Time Frame: T3, during the procedure (10 min after the beginning of the hydrotherapy session)]: rescue dose medication administration.
- 5) Sedation level [Time Frame: T2, before the procedure, upon arrival in the hydrotherapy room, T3, during the procedure (10 min after the beginning of the hydrotherapy session), T4, immediately after the procedure before leaving the hydrotherapy room]: Ramsay sedation scale.
- 6) Baseline anxiety level [Time Frame: T1, 30 minutes before the procedure, in the patient's room]: Modified Smith Scale.

# **FEASIBILITY**

The setting of the study is the main referral center for pediatric burns in Quebec. It receives nearly 60 admissions during the period when there is a higher incidence of burns (April to October) and almost 100 admissions per year. The investigators will be able to access the population for the study given the PI's affiliation to the research center of this setting. Moreover, stakeholders in the pain clinic and surgical-trauma unit are aware of the study, and participated in all stages of the prototype development.

### POSSIBLE PITFALLS AND SOLUTIONS

It is unknown whether the VR is a feasible distraction technique in young children/infants aged between 2 months and 2 years old. The pilot study will help inform the investigators about the visual tracking in infants during painful medical procedures. Upon completion of the pilot study, it will be decided whether to include or not the young population in the larger trial.

### CONTRIBUTION AND EXPECTED RESULTS

Despite growing interest in the field, procedural pain management in children remains suboptimal and the importance of developing more effective methods is required. This project will provide

preliminary evidence on the feasibility, acceptability, and preliminary efficacy of non-pharmacological methods of procedural pain management through the development and testing of innovative interventions. VR distraction could be an interesting method to relieve pain, easy to use and without known side effects. The investigators hope that it could reduce the need for opioids and anxiolytics in burn children and decrease the pain related to the procedures while providing a less traumatizing hospital experience, which is often the first for children under 5 years old. The expected results have a direct effect on physical (pain, comfort) and psychological (anxiety) health of the child. In addition, clinical implications may include other indicators of quality of care and economic benefits such as duration of the hydrotherapy session, the amount of opioids and anxiety drugs administered, the use of coanalgesics, the number of professionals required in the hydrotherapy room and duration of wound healing.

## DATA ANALYSIS PLAN

Descriptive statistics will be performed for sociodemographic and clinical variables, comfort levels and the satisfaction of health professionals. Non-parametric inferential statistics will be used to compare the mean differences in pain scores before, during and after the procedure as well as for anxiety and level of sedation. Since the use of rescue medication is a potential indication of a treatment failure, the analysis will be supplemented by an analysis comparing the proportion of patients receiving rescue medication anytime during the procedure. Interpretation of the analyses will be made with reference to the data regarding rescue medication use. Data collected on dichotomous variables will be analyzed using a chi-square test and post-hoc analyses if the results are statistically significant.

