### **BACKGROUND**

The burden of burns and pain. Burn injuries are among the leading causes of visits to the emergency department and hospitalizations in young children. They mostly result from scalds and contact with household appliances. Regardless the cause of the injury, dressing changes and hydrotherapy sessions for burn injuries are associated with extreme pain. The management of acute pain experienced during hydrotherapy sessions in patients with burn injuries, called procedural pain, remains a major challenge for healthcare professionals. Pain can have several short term effects on the child on the development, mood, sleep, appetite, school performance, anxiety and distress levels. In the long term, it can decrease the pain threshold, cause stress disorders, affect social behavior and seeking of medical services. In burn injuries, pain is often accompanied by great anxiety, which in turn, decreases pain tolerance. To relieve pain and anxiety, clinicians usually rely on pharmacological agents via the administration of high doses of opioids and anxiolytics. The use of these medications can cause deep sedation in children, and many side effects such as nausea, vomiting, and respiratory depression. Also, despite the growing use of opioids, patients report pain of more than 7 on a scale of 0-10 during their dressing changes and hydrotherapy sessions. Multimodal approaches combining medication and non-pharmacological interventions should be explored to reduce pain and anxiety associated with painful procedures.

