**Measures**. Measures of baseline pain and anxiety will be recorded at T1, 30 minutes before the procedure, in the patient's room. Measures for procedural pain, anxiety and sedation level will be taken at: T2, before the procedure, upon arrival in the hydrotherapy room, T3, during the procedure (10 min after the beginning of the hydrotherapy session), T4, immediately after the procedure before leaving the hydrotherapy room and T5, 30 minutes after the procedure in the patient's room. The patient's comfort level will also be assessed during the procedure at T3. Finally, the acceptability of the intervention will be assessed through a questionnaire comprising items on the acceptability and satisfaction of the healthcare professionals at T4. The same measures will be recorded for each participant for up to three hydrotherapy sessions. The primary outcome will be the acceptability of the intervention. Comparisons will be made between pain and anxiety levels for the same order of session.

**A) Primary Outcome Measure**: Acceptability [Time Frame: T4, immediately after the procedure before leaving the hydrotherapy room]: To assess the acceptability including the satisfaction of healthcare professionals regarding the use of the VR prototype during the hydrotherapy session. Pre-tested tailored questionnaire including satisfaction and acceptability outcomes (tolerance, positive and negative aspects, secondary effects).

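### Pain, anxiety and comfort are scored from behaviour, but the plan never reads them against the sedation score taken at the same time

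*Combined protocol and SAP*

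**What the plan says.** The list of secondary outcome measures names "Face, Legs, Activity, Cry and Consolability (FLACC") for pain, a procedural behaviour checklist (PBCL) for anxiety, and for comfort a "Behavioural observation scale of comfort level for child burn victims" (OCCEB-BECCO). By their names, all three are scored from what an observer sees. No self-report pain scale is listed, although children up to 10 years are eligible. The documents do not say how the T1 anxiety measure, the "Modified Smith Scale", is scored, so it is left out of this point.

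Sedation is scored on the "Ramsay sedation scale" at T2, T3 and T4. FLACC and PBCL are taken at those same times, and comfort is taken at T3.

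The Background says of the usual opioids and anxiolytics: "The use of these medications can cause deep sedation in children". The eligibility criteria exclude children who are unconscious or intubated during the session but give no Ramsay cut-off.

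Under Data Analysis Plan, "Non-parametric inferential statistics will be used to compare the mean differences in pain scores before, during and after the procedure", and anxiety and sedation are compared in the same manner. Comfort is only described. Interpretation is to refer to rescue medication use; sedation has no such role.

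**The concern.** A child who is too drowsy to grimace, kick or cry scores low on a behavioural scale whether or not the procedure hurts. The protocol itself names deep sedation as an effect of the background drugs, and under hypothesis (b) virtual reality is combined with analgesics. The design is single-arm, so no concurrent group would expose such an effect.

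Comparing average sedation over time shows whether sedation shifted in the group. It does not show whether the children with low FLACC scores were the sedated ones, and that is what a reader needs in order to judge a low pain score.

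At stake are the secondary efficacy question and hypothesis (b). The section on expected results promises preliminary evidence of efficacy, and the section on pitfalls looks ahead to a larger trial.

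**Working it through.** **Reading the plan.** The documents give no significance level, SD, effect size or sedation rate, so there is no figure to reproduce. The first check is whether the plan links sedation to each behavioural outcome.

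| Outcome | Scored from behaviour | Concurrent Ramsay | Planned analysis | Linked to sedation |
|---|---|---|---|---|
| Pain (FLACC) | yes | T2, T3, T4 | non-parametric comparison over time | no |
| Anxiety (PBCL) | yes | T2, T3, T4 | same | no |
| Comfort (OCCEB-BECCO) | yes | T3 | descriptive | no |

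The outcome list stops sedation at T4. The Measures text ("Measures for procedural pain, anxiety and sedation level will be taken at") goes on to a schedule that includes T5. The two should be reconciled, but this point needs only T2 to T4.

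**How large could the effect be?** All inputs here are assumptions:
- 20 children, the top of the planned range of 15 to 20;
- FLACC scored 0-10, SD 2, correlation 0.5 between T2 and T3;
- a share q deeply sedated, each of them scoring 0, 1 or 2 (mean 1);
- paired Wilcoxon signed-rank test, two-sided 5%.

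If true mean pain is 6 at T3 and sedation occurs only at T3, the expected T3 mean is 6 - q × (6 - 1) = 6 - 5q.

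- *Pain 6 at both times:* the apparent change is -5q, which is -0.5, -1.25 and -2.0 for q = 10%, 25% and 40%.
- *Pain rising from 4 to 6:* the apparent change is 2 - 5q, which is +1.5, +0.75 and 0.

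Simulated share of trials declaring a significant reduction that is not real:

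| True mean T2 → T3 | Sedated at | 10% | 25% | 40% |
|---|---|---|---|---|
| 6 → 6 | T3 only | 9% | 35% | 73% |
| 5 → 6 | T3 only | 0.2% | 3% | 21% |
| 4 → 6 | T3 only | 0% | 0.1% | 2% |
| 6 → 6 | same children at T2 and T3 | 2-3% | 2-3% | 2-3% |

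With nobody sedated and no true change, the rate in that direction is 2.6%. With 15 children, the first row becomes about 7%, 28% and 57%.

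In the 4 → 6 case the error goes the other way. The real rise is detected in about 98% of trials with nobody sedated, but in about 23% with 25% sedated at T3.

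**A milder model.** Here sedation cuts the score to a half or a quarter of its value, with child mean 6, between-child and within-child SD 1.5, and equal true pain at both times. For 20 children, false reductions occur in 17-23% of trials with 20% sedated and in 50-70% with 40% sedated. For 15 children the figures are 12-19% and 40-56%. This model also assumes flat pain and sedation at the second time only, so it does not test those two assumptions.

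**The case against.** The strongest reply is that a false reduction needs pain to be as high on arrival as during the procedure. T2 precedes the procedure and T3 falls 10 minutes into it. The Background calls these sessions extremely painful, with reported scores above 7 out of 10. If pain rises by 2 points, false reductions almost vanish. They also vanish if the same children are already sedated on arrival. This stands, and it rules out quoting one error rate as the expected one. It does not remove the problem, because a blunted rise can be read as relief just as a fall can.

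A reader might infer from the flat-pain figures that a significant fall in FLACC would probably be a sedation artefact. The documents do not support that: they give neither the T2 pain level nor any sedation rate.

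Other safeguards are partial:
- The exclusion of unconscious or intubated children removes the extreme case but not lesser deep sedation.
- Rescue medication use does not show how sedated a child was from standard drugs, and rescue drugs could themselves lower later scores.
- Reporting sedation over time would show a parallel shift in the group, but not which children had it.

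It is also fair to say that the single-arm design limits any claim for hypothesis (b) whatever the sedation, and that acceptability is the primary outcome. A reader might infer that the acceptability or feasibility result is distorted too. Nothing in the documents shows how sedation would alter the professionals' questionnaire. For comfort, which is not tested, the risk is misreading rather than a false test.

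**Conclusion.** The gap is real and modest. Sedation is collected beside behavioural scores that it can lower, and the plan neither shows the two together nor says how to read a low score in a deeply sedated child. The effect is confined to secondary outcomes. Its size cannot be fixed from the documents: with 10-40% deeply sedated at T3 only, false reductions range from about 9-73% with flat pain at 6 down to 0-2% with a 2-point rise, where the harm is a hidden rise instead. They stay at 2-3% if the same children are sedated at both times and pain is flat at 6. These figures rest on the assumed scale, SD, correlation and sedated scores. They show that the answer depends on who was sedated and when, which the planned analysis would not show.

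**What to change.** Add to the Data Analysis Plan:

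1. A descriptive table or plot of FLACC and PBCL by concurrent Ramsay level at T2, T3 and T4, and of OCCEB-BECCO by Ramsay level at T3.
2. A statement that pain, anxiety and comfort results will be interpreted with reference to concurrent sedation as well as rescue medication, and that low scores in deeply sedated children will not count as evidence of pain relief.
3. Optionally, a repeat of the pain and anxiety comparisons that leaves out observations above a Ramsay level fixed before the data are seen. Label it supportive only. The wording of the main result should not depend on whether it agrees, because with so few children disagreement may reflect only lost power.

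The cost is a few lines of text and one table with small cells. No new data are needed and no planned analysis is replaced. The optional analysis conditions on a post-baseline measure that may itself respond to pain or to the intervention.

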## **METHODS**

**Design**. Single-arm pilot study.

**Sample and Setting**. Participants will be recruited through convenience sampling upon admission to the surgical-trauma burn unit. The unit has a hydrotherapy room for inpatients and outpatients. Healthcare professionals usually present during hydrotherapy are: a burn wound care nurse, a nurse clinician from the pain clinic, an anesthetist, a physical therapist and an orderly. The size of the total desired sample is 15 to 20 participants depending on the recruitment rate since it is a pilot study. The study will take place in the hydrotherapy room of the CHU St. Justine, a large pediatric university teaching hospital in Montreal where the VR prototype is installed.

Eligibility criteria. Inclusion criteria: children from 2 months to 10 years old, with a burn injury, requiring a hydrotherapy session for burn wound care, and accompanied by a consenting parent/legal tutor who can understand, read, and write either French or English. Exclusion criteria: 1) Admitted to the intensive care Unit, 2) Neuro-cognitive disability that precludes children from interacting with the distraction intervention, 3) Unconscious or intubated during hydrotherapy session, 4) Suffering from epilepsy (considering the nature of the intervention), 5) Allergic to opioids or other analgesics used for standard pharmacological treatment.

**Intervention**: The child will visualize and interact with the virtual environment throughout the hydrotherapy session. VR prototype developed by the SAT will be used as the experimental intervention. It has a wide screen installed at the end of the hydrotherapy tank offering a 150-degree field view, on which appears a game allowing the child to have the immersive entertainment experience without the need to wear a helmet or 3D glasses. The child or a proxy, depending on age and burn site, will have the opportunity to interact with the game. The interactive component is not mandatory for the immersive and distractive experiences provided by the prototype. Video

games tailored to the child's age and injury, different from the commercially available ones, will be adapted to each age-group of children recruited with control over the speed of movement to avoid motion sickness.

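### A chi-square test does not suit yes/no rescue data from one arm with up to three sessions per child, and the comparison it would serve is not named

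*Combined protocol and SAP*

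**What the plan says.** - **Design** (Methods): "Single-arm pilot study", with 15 to 20 children.
- **Repeat sessions** (Methods, Measures): "The same measures will be recorded for each participant for up to three hydrotherapy sessions". The only rule for handling them is "Comparisons will be made between pain and anxiety levels for the same order of session", which names pain and anxiety but not rescue.
- **Rescue analysis** (Data Analysis Plan): a supplementary analysis "comparing the proportion of patients receiving rescue medication anytime during the procedure", and then "Interpretation of the analyses will be made with reference to the data regarding rescue medication use". What the proportion is compared with is not stated.
- **Test** (Data Analysis Plan): "Data collected on dichotomous variables will be analyzed using a chi-square test and post-hoc analyses if the results are statistically significant".
- **Rescue as an outcome** (Secondary Outcome Measures, item 4): "Analgesic requirement [Time Frame: T3, during the procedure (10 min after the beginning of the hydrotherapy session)]: rescue dose medication administration".
- **Standard treatment** is the comparator in the secondary research question (Aim) and in hypothesis b, in both cases for pain and anxiety. No control group, historical series or reference rate is described anywhere.

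**The concern.** A chi-square test needs at least two groups of independent observations. This design has one group, and the natural subdivisions of its data are not independent, because one child can supply several sessions. The plan does not say which table is to be tested or how a child with two or three sessions enters it. An analyst would have to choose, and the choice decides whether the test is too conservative or too liberal.

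The plan calls rescue a possible sign of treatment failure and reads its other analyses against it. An unclear rescue proportion therefore affects how the pain, anxiety and sedation results are read. The two descriptions of when rescue is counted add to the uncertainty.

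**Working it through.** **Inputs.** From the documents: one arm, 15 to 20 children, up to three sessions each. Not given, and assumed here: two-sided 5% tests, the rescue rates, the within-child correlation and the number of completed sessions. The plan offers no figure of its own to reproduce.

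**Step 1: which comparisons are possible?** There are three candidates.

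- *Against standard treatment:* no data are supplied, so this is not possible.
- *Between sessions:* possible, but the same children are in each column.
- *Between groups of children:* possible, but independent only if each child counts once.

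**Step 2: sessions compared by ordinary chi-square.** With session counts x_j and common proportion p̄, the statistic is X² = Σ (x_j − n p̄)² / [n p̄(1 − p̄)], on 2 df. If the yes/no results within a child have correlation ρ, differences between sessions have variance smaller by a factor (1 − ρ), and X² ignores this. The type I error is then roughly 0.05^[1/(1 − ρ)]:

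- ρ = 0.3: 0.05^1.43 ≈ 0.014
- ρ = 0.5: 0.05^2 = 0.0025

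Simulation under a beta-binomial model (rates 0.3 and 0.5, 15 or 20 children) gives 0.015 to 0.016 and 0.003 to 0.004.

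A second simulation used a latent normal model, in which latent r exceeds the correlation between the yes/no results, so the two scales should not be matched. Three complete sessions; type I error at a 30% rate; power for rates of 50%, 35% and 20%:

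| n | latent r | type I error: chi-square / Cochran's Q | power: chi-square / Cochran's Q |
|---|---|---|---|
| 20 | 0 | about 5% / about 5% | 42% / 40% |
| 20 | 0.5 | 1.6% / 5.1% | 37% / 55% |
| 20 | 0.7 | 0.5% / 4.9% | 34% / 66% |
| 15 | 0 | about 5% / about 5% | 32% / 31% |
| 15 | 0.5 | 1.5% / 4.9% | 26% / 42% |
| 15 | 0.7 | 0.5% / 4.4% | 22% / 51% |

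**Step 3: incomplete sessions.** Suppose 20, 15 and 10 children have sessions 1, 2 and 3. At r = 0.5, 0.7 and 0.9, power is 23%, 20% and 18% for chi-square, against 28%, 32% and 40% for a Cochran-Mantel-Haenszel test with child as stratum. At r = 0 the order reverses (28% against 21%). The stratified test is itself conservative: type I error about 3.6%, 2.8% and 1.0% at the same three correlations.

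**Step 4: sessions pooled between two sets of children.** With three sessions per child the variance is inflated by 1 + 2ρ, and the type I error is about 2[1 − Φ(1.96/√(1 + 2ρ))]:

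- ρ = 0.3: 1.96/√1.6 = 1.55, giving about 0.12
- ρ = 0.5: 1.96/√2.0 = 1.39, giving about 0.17
- ρ = 0.7: 1.96/√2.4 = 1.27, giving about 0.21

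Beta-binomial simulation gives 0.12 to 0.13, 0.17, and 0.21 to 0.22.

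**Step 5: one record per child.** Independence holds, but counts are small. Two groups of 10 at a 30% rate give an expected 10 × 0.3 = 3 rescued children per group, which is weak ground for the chi-square approximation.

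**Step 6: the windows side by side.** The outcome list ties rescue to T3, ten minutes into the session. The analysis plan counts it at any time in the procedure. A dose given at another moment counts under the second and is unclear under the first.

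**The case against.** The strongest reply is that no comparison between sessions is planned. The same-order rule keeps comparisons within a session order, and post-hoc testing need not mean three sessions: the plan also speaks of before, during and after the procedure. This stands. The figures in steps 2 and 3 show what would happen under one possible reading; they do not measure a defect in a stated analysis. Three complete sessions for every child is also the most favourable case for Cochran's Q.

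The gain from paired tests is not general either. With two sessions and 12 or fewer complete pairs, ordinary chi-square had more power than a mid-p McNemar test at every correlation tried.

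Four stronger readings are tempting, and the documents do not support them.

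- *The plan inflates false positives, or is simply conservative.* The direction depends on a contrast that is not stated.
- *Rescue will be tested against standard treatment.* The Aim and hypothesis b name that comparator for pain and anxiety only.
- *A child counts as rescued if any session had rescue.* At 30% per session with independent sessions, that would raise the proportion to 1 − 0.7³ = 66%. But the plan counts patients and refers to the procedure, which elsewhere means one session, so a per-session proportion is the more natural reading. An explicit rule is still absent.
- *The two windows flatly contradict each other.* Item 4 also refers to the procedure, and its parenthesis may only define the T3 label. The two descriptions need reconciling, and no more can be claimed.

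**Conclusion.** The point holds in limited form. A chi-square test for dichotomous data is a poor general rule here. Between sessions it ignores pairing, between children with pooled sessions it is liberal, and with one record per child the counts are small. The comparison for rescue is not named, and the data allow none with standard treatment.

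The size rests wholly on assumed rates, correlations and session numbers. At latent correlation 0.5 with three complete sessions, the type I error is about 1.5% instead of 5%; at correlation 0 there is no loss. Pooling between children gives about 12% to 22% at within-child correlations of 0.3 to 0.7. Placing rescue under the chi-square sentence is an inference, though a reasonable one.

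The consequence is modest. Rescue is a supplementary secondary outcome in a pilot, and "The primary outcome will be the acceptability of the intervention". The change is worth making because it is cheap and the other results are read against rescue.

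**What to change.** For rescue, replace the chi-square sentence with:

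> The proportion of children receiving rescue medication is reported separately for sessions 1, 2 and 3, with the number of children who had that session and an exact (Clopper-Pearson) 95% CI; this is the main analysis. Sessions of one child are not treated as independent. Any comparison between sessions is exploratory and within child (Cochran's Q in children with all three sessions). Any comparison between children uses the first session only and Fisher's exact test. No comparison with standard treatment is made.

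Reconcile the rescue window in Secondary Outcome Measures, item 4, with the one in the Data Analysis Plan, and use the same definition in both.

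**Cost.** A few sentences, and no new data unless the reconciled window needs a different recording field. Intervals will be wide: 5/20 gives 25% (9% to 49%), 3/15 gives 20% (4% to 48%) and 3/10 gives 30% (7% to 65%). Within-child testing adds little or no power when correlation is low or few children have complete sessions. Children who need a later session may differ from the rest, so the per-session proportions are descriptive and do not show a trend within the same group.
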